3.1.2 Exclusion criteria

- Known hypersensitivity or allergic response to Flutamide
- Severe hepatic impairment (serum ALT level $>2x$ normal or serum AST level $>2x$ normal)
- Pre-existing diagnosis of hypogonadism (serum total testosterone < 150 ng/dL) prior to starting hormone therapy for prostate cancer, or treatment with testosterone supplementation therapy within 12 months prior to enrollment
- Major medical or psychiatric illness which, in the investigator's opinion, would prevent completion of treatment and would interfere with follow up.

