4.5 Clinical Assessments / Study Calendar A

In order to minimize the need for research-only in-person visits, telemedicine visits may be substituted for in person clinical trial visits or portions of clinical trial visits where determined to be appropriate and where determined by the investigator not to increase the participants' risks. Prior to initiating telemedicine for study visits the study team will explain to the participant, what a telemedicine visit entails and confirm that the study participant is in agreement and able to proceed with this method. Telemedicine acknowledgement will be obtained in accordance with the Guidance for Use of Telemedicine in Research. In the event telemedicine is not deemed feasible, the study visit will proceed as an in-person visit. Telemedicine visits will be conducted using HIPAA compliant method approved by the Health System and within licensing restrictions.

A synopsis of the study procedures is shown below:

Parameter	Pre-Study	Pre-androgen suppression	PRE-BIOPSY / IMPLANT			BIOPSY / IMPLANT DAY ^A	POST-BIOPSY / IMPLANT	
			-180 to 0 DAYS ^G	-10 to 0 DAYS	-12 TO -6 HOURS		4 weeks (+/-7 days)	6 months (+/-45 days)
H&P, LABS (CMP)	X							
Study Eligibility	X							
MRI of prostate	X							
Androgen suppression w/ GnRH analogue	X ^G		X ^G					
Study Drug Admin (250mg vs Placebo)					X			
LABS (PSA / Testosterone)	X		X ^{C, H}				X	X
Plasma for cell free DNA ^B		X ^D		X ^{C, D}			X ^D	X ^D
Urine (50 mL)		X ^D		X ^{C, D}			X ^D	X ^D
Plasma for hydroxyflutamide ^F				X ^E		X		

^A Day of biopsy and brachytherapy implant procedure.

^B Streck Tubes (10 mL) x 4

^C Samples may be obtained either pre- or post-flutamide ingestion, but prior to biopsy/implant

^D These items are separate (optional) consent for exploratory analysis.

^E -10 to 0 Day Timepoint for non-randomized cohort (n=6) only; sample taken prior to hydroxyflutamide ingestion

^F Heparin/Green Top Tubes (4 mL) x 1

^G Patient may be enrolled already on GnRH analogue, or receive after enrollment. Brachytherapy to be performed anytime within 180 days from initiation of androgen suppression provided the patient's testosterone level is < 50 ng/dL.

^H PSA and Testosterone should be done at least 30 days after Initiation of Androgen Suppression and within 180 days prior to brachytherapy.

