9.0 Description of the Drug

Flutamide is approved by the US Food and Drug Administration for use in patients with (Jewett) stage B2-C prostate cancer (i.e. AJCC stage T1c – T3b), in conjunction with androgen deprivation and radiation therapy.

Flutamide Description

Flutamide capsules contain Flutamide, an acetanilid, nonsteroidal, orally active antiandrogen having the chemical name, α,α,α -trifluoro-2-methyl-4'-nitrom-propionotoluidide.

Each capsule contains 125 mg Flutamide. The compound is a buff to yellow powder with a molecular weight of 276.22 and the following structural formula:

C11H11F3N2O3

In addition, each capsule contains the following inactive ingredients: corn starch, lactose monohydrate, magnesium stearate, povidone, and sodium lauryl sulfate. Gelatin capsule shells may contain gelatin, silicon dioxide, sodium lauryl sulfate, titanium dioxide, FDA/E172 Red Iron Oxide, FDA/E172 Yellow Iron Oxide, and black ink containing pharmaceutical glaze (modified) in SD-45, synthetic black iron oxide, Nbutyl alcohol, SDA-3A alcohol, FD&C Blue No.2 Aluminum Lake, FD&C Red No.40 Aluminum Lake, FD&C Blue No.1 Aluminum Lake, and D&C Yellow No.10 Aluminum Lake.

Clinical Pharmacology General

In animal studies, Flutamide demonstrates potent antiandrogenic effects. It exerts its antiandrogenic action by inhibiting androgen uptake and/or by inhibiting nuclear binding of androgen in target tissues or both.

Prostatic carcinoma is known to be androgen-sensitive and responds to treatment that counteracts the effect of androgen and/or removes the source of androgen, e.g., castration. Elevations of plasma testosterone and estradiol levels have been noted following Flutamide administration. **Pharmacokinetics**

Absorption

Analysis of plasma, urine, and feces following a single oral 200 mg dose of tritium-labeled Flutamide to human volunteers showed that the drug is rapidly and completely absorbed. Following a single 250 mg oral dose to normal adult volunteers, the biologically active alpha-hydroxylated metabolite reaches maximum plasma concentrations in about 2 hours, indicating that it is rapidly formed from Flutamide. Food has no effect on the bioavailability of Flutamide.

Distribution

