Race There are no known alterations in Flutamide absorption, distribution, metabolism, or excretion due to race.

Renal Impairment Following a single 250 mg dose of Flutamide administered to subjects with chronic renal insufficiency, there appeared to be no correlation between creatinine clearance and either Cmax or AUC of Flutamide. Renal impairment did not have an effect on the Cmax or AUC of the biologically active alpha-hydroxylated metabolite of Flutamide. In subjects with creatinine clearance of < 29 mL/min, the half-life of the active metabolite was slightly prolonged. Flutamide and its active metabolite were not well dialyzed. Dose adjustment in patients with chronic renal insufficiency is not warranted.

Hepatic Impairment No information on the pharmacokinetics of Flutamide in hepatic impairment is available (see **BOXED WARNING, Hepatic Injury**).

Women, Pediatrics Flutamide has not been studied in women or pediatric subjects. **Drug-Drug Interactions**

Interactions between Flutamide capsules and LHRH-agonists have not occurred. Increases in prothrombin time have been noted in patients receiving warfarin therapy (see **PRECAUTIONS**).

Clinical Studies

Flutamide has been demonstrated to interfere with testosterone at the cellular level. This can complement medical castration achieved with LHRH-agonists which suppresses testicular androgen production by inhibiting luteinizing hormone secretion.

The effects of combination therapy have been evaluated in two studies. One study evaluated the effects of Flutamide and an LHRH-agonist as neoadjuvant therapy to radiation in stage B2-C prostatic carcinoma and the other study evaluated Flutamide and an LHRH-agonist as the sole therapy in stage D2 prostatic carcinoma.

Stage B2-C Prostatic Carcinoma

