The effects of hormonal treatment combined with radiation was studied in 466 patients (231 Flutamide capsules + goserelin acetate implant + radiation, 235 radiation alone) with bulky primary tumors confined to the prostate (stage B2) or extending beyond the capsule (stage C), with or without pelvic node involvement. In this multicentered, controlled trial, administration of Flutamide capsules (250 mg t.i.d.) and goserelin acetate (3.6 mg depot) prior to and during radiation was associated with a significantly lower rate of local failure compared to radiation alone (16% vs. 33% at 4 years, $P < 0.001$). The combination therapy also resulted in a trend toward reduction in the incidence of distant metastases (27% vs. 36% at 4 years, $P = 0.058$). Median disease-free survival was significantly increased in patients who received complete hormonal therapy combined with radiation as compared to those patients who received radiation alone (4.4 vs 2.6 years, $P < 0.001$). Inclusion of normal PSA level as a criterion for disease-free survival also resulted in significantly increased median disease-free survival in patients receiving the combination therapy (2.7 vs. 1.5 years, $P < 0.001$).

Stage D2 Prostatic Carcinoma

To study the effects of combination therapy in metastatic disease, 617 patients (311 leuprolide + Flutamide, 306 leuprolide + placebo) with previously untreated advanced prostatic carcinoma were enrolled in a large multicentered, controlled clinical trial.

Three and one-half years after the study was initiated, median survival had been reached. The median actuarial survival time was 34.9 months for patients treated with leuprolide and Flutamide versus 27.9 months for patients treated with leuprolide alone. This 7 month increment represents a 25% improvement in overall survival time with the Flutamide therapy. Analysis of progression-free survival showed a 2.6 month improvement in patients who received leuprolide plus Flutamide, a 19% increment over leuprolide and placebo.

Indications and Usage for Flutamide

Flutamide capsules are indicated for use in combination with LHRH-agonists for the management of locally confined Stage B2-C, and Stage D2 metastatic carcinoma of the prostate. **Contraindications**

Flutamide capsules are contraindicated in patients who are hypersensitive to Flutamide or any component of this preparation.

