Flutamide capsules are contraindicated in patients with severe hepatic impairment (baseline hepatic enzymes should be evaluated prior to treatment).

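### Minor safety alignment: the hypersensitivity exclusion is narrower than the plan's own contraindication, and the liver-enzyme exclusion sets no maximum age for the result at dosing

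*Combined protocol and SAP*

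**What the plan says.** Two exclusions in Section 3.1.2 concern the safety of the drug. One is "Known hypersensitivity or allergic response to Flutamide". The other begins "Severe hepatic impairment (serum ALT level" and sets the limit at more than twice normal for either ALT or AST. Neither exclusion states when it must be assessed.

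Section 9.0 describes the product. On allergy it says "Flutamide capsules are contraindicated in patients who are hypersensitive to Flutamide or any component of this preparation". On content it says "each capsule contains the following inactive ingredients: corn starch, lactose monohydrate, magnesium stearate, povidone, and sodium lauryl sulfate", and then lists gelatin and several dyes as possible shell ingredients. On the liver it makes severe impairment a contraindication and adds that "baseline hepatic enzymes should be evaluated prior to treatment". It also says "No information on the pharmacokinetics of Flutamide in hepatic impairment is available" and points to a boxed warning on hepatic injury.

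The calendar in Section 4.5 has one row for the chemistry panel (CMP), with a single mark under Pre-Study, a column with no day range. Footnote G says "Patient may be enrolled already on GnRH analogue, or receive after enrollment", and allows the implant up to 180 days after suppression starts. Footnote H says "PSA and Testosterone should be done at least 30 days after Initiation of Androgen Suppression and within 180 days prior to brachytherapy". The important notes to Section 4.5 take a man off protocol if testosterone measured 0-7 days before implant is above castrate level. Under Section 5.1, study drug is taken 6-12 hours before brachytherapy.

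**The concern.** There are two gaps, both between the screening list and the drug section or the calendar.

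The first is one of wording. A screener who applies Section 3.1.2 as written can enrol a man with a known allergy to a capsule ingredient, for whom Section 9.0 contraindicates the capsule. No other exclusion covers him; the general one concerns major illness that would prevent completion of treatment or interfere with follow-up.

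The second is one of timing. The liver-enzyme exclusion is tested once, and the plan puts no limit on the time between that test and the dose. A man whose enzymes rise above twice normal in between would be dosed without anyone knowing, although he would fail the criterion if it were applied that week. Routine care cannot be assumed to close the gap. Section 7.0 refers to standard pre-treatment assessments in a Section 4.7, but the text has no such section, so the documents do not say whether liver tests are among them.

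**Working it through.** The plan gives no figure of its own here. The check is a comparison of texts and a calculation of dates.

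**Hypersensitivity.** Section 3.1.2 covers flutamide only. Section 9.0 covers flutamide and every component of the capsule. The difference is the set of inactive ingredients that Section 9.0 itself lists. The documents give no prevalence of allergy to any of them; few men are likely to be affected.

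**Age of the liver result at dosing.** The inputs are:
- day 0 is the start of androgen suppression;
- the implant is no earlier than day 30, because the PSA and testosterone sample must be at least 30 days after the start and before the implant (footnote H);
- the implant is no later than day 180 (footnote G);
- dosing is 6-12 hours, or 0.25-0.5 day, before the implant (Section 5.1);
- assumption: for a man who starts suppression after enrolment, the CMP is drawn on day 0 or *g* days before it. The plan sets no limit on *g*.

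For that man:
- youngest possible result: 30 − 0.5 = 29.5 days, or about 30 days, with *g* = 0;
- oldest possible result: 180 − 0.25 + *g* = 179.75 + *g* days, which exceeds 180 once *g* is 1 day or more and has no upper limit.

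For a man already on a GnRH analogue whose CMP is drawn *s* days after it started, the age is at most about 180 − *s* days and there is no minimum.

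With ALT and AST on a sample taken 0-7 days before implant and before study drug, the age at dosing is at most 7 − 0.25 = 6.75 days for every man.

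**Reading of the calendar.** The table was extracted from PDF and its columns may have shifted. A shift would not create a second CMP mark or a window for it, and no footnote or other section supplies one.

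**The case against.** The case against has four parts.

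- The wider allergy warning is already in the same protocol, and a history and physical is required at Pre-Study. A careful investigator would not give the capsule to a man known to be allergic to one of its ingredients. This stands as a reason to call the mismatch editorial. It does not make the screening list correct.
- A reader might infer that the liver schedule contradicts Section 9.0. It does not. Section 9.0 asks for baseline enzymes before treatment and sets no day limit, and the Pre-Study CMP meets that. Nor does the text show an intention to re-screen enzymes: where the plan wants a check close to the implant, as for testosterone, it says so. The point is a gap in the design and not an inconsistency.
- A reader might also want to say how many men would be dosed with raised enzymes. The documents give no rate of enzyme rise between screening and dosing, so no such number can be supported. Crossing a laboratory threshold is also not the same as harm. Section 7.0 rates lasting toxicity from a single 250 mg dose as very unlikely, against standard dosing three times a day for 4 months or more.
- The upper end of the age range is a worst case. The plan does not give the typical interval or the share of men already on a GnRH analogue at enrolment, for whom the result may be recent.

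All of this limits the weight of the point. None of it supplies the missing age limit.

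**Conclusion.** The point holds as a minor, optional safety improvement. The hypersensitivity exclusion is narrower than the plan's own contraindication. The liver-enzyme exclusion rests on a result of unlimited age: about 30 to more than 180 days at dosing for a man who starts suppression after enrolment, assuming his CMP is drawn on or before that start. Confidence is high for these facts of the text. No claim is made about how many men would be affected or harmed, because the documents do not support one. The endpoint, sample size and stopping rule are untouched. It is worth changing only because the change is small and a sample close to the implant is already needed.

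**What to change.** 1. In Section 3.1.2, extend the hypersensitivity exclusion so that it covers flutamide *or any component of the preparation*.
2. Set a maximum age for ALT and AST before study drug. The simplest way is to add both to the testosterone sample that the 0-7 day rule in Section 4.5 needs. Draw it before study drug and have the result in hand before dosing, since calendar footnote C otherwise allows sampling after ingestion. In the randomised phase, do this before randomisation where possible, so that the 12:6 allocation is not disturbed. Seven days is convenient; the window itself is the sponsor's clinical choice.
3. State the consequence. If either enzyme exceeds twice normal, study drug is withheld and the man is replaced as a pre-procedure drop-out under Section 6.2. This needs a sentence of its own, because Section 13.0 lists only withdrawn consent and noncompliance as reasons for withdrawal.

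The cost is one phrase, one calendar footnote, one sentence and two analytes. If testosterone would otherwise be taken only at the earlier time that footnote H permits, an extra blood draw may be needed, though the 0-7 day rule already implies one. An occasional man will be screened out, some of them for a transient rise.

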4.0 Protocol Design

This will be a prospective, single-center, two-phase study to assess the efficacy of single pulsed-dose Flutamide in creating DSBs in prostate cancer within patients receiving central androgen suppression and brachytherapy. The initial phase is a 6-patient single-arm run-in phase to test feasibility and rule out futility of the intervention. All patients within the run-in phase will receive 250mg Flutamide prior to brachytherapy and prostatic biopsy. Biostatistician will be consulted upon completion of run-in phase. If futility is ruled out (>1 patients with DSBs on biopsy), then accrual will continue in the randomized, double-blind phase. Subjects will be randomized in a 2:1 ratio (12:6 patients), for total of 18 patients randomized receiving Flutamide and 6 patients receiving placebo. Thus, total evaluable patients including both phases (non-randomized/run-in plus randomized) will be 24 patients, with 30 enrolled to ensure minimum of 24 evaluable.

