5.3 Biopsy and implant procedure

In the operating room, patient will be anesthetized per clinical routine for brachytherapy, and placed in dorsal lithotomy position. A transrectal ultrasound (TRUS) probe will be placed into the rectum for prostate visualization. The perineum will be prepped in sterile fashion.

TRUS images will be captured and fused with the MRI to identify the regions of prostate cancer involvement to be targeted. Transperineal biopsy will be carried out under TRUS guidance, with ≥ 4 cores targeted per MRI-defined region of involvement / clinically palpable region. The number of biopsy cores taken is not to exceed 12 (twelve) cores.

Following completion of the biopsy portion of the procedure, patient will undergo brachytherapy per usual clinical routine.

Biopsy samples will be processed for paraffin embedding and pathologic confirmation of tumor tissue presence (handled and stored by [name] laboratory). Analyses for DSBs will be performed using assays for TUNEL, 53bp1, and gamma h2ax. Approximately 1/3 of tissue will be frozen and set aside for future potential laser dissection capture for RNA sequencing (handled and stored in [name] laboratory).

Staff from [name] laboratory will arrange collection and archiving of diagnostic material. This will consist of the slides and/or paraffin blocks from the biopsies (both pretreatment and postflutamide/pre-brachytherapy).

Central pathology review will be performed for patients who have agreed / opted to allow us access to any post-treatment biopsies, if performed in routine clinical care, and retrospective review of baseline diagnostic pathologies. Formalin fixed biopsy tissue may be used for correlative DNA methylation analysis.

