6.2 Sample Size Justification and Accrual

This is a pilot trial, and will be utilized to design a larger study to establish measures for such parameters with a reasonable level of precision. We will enroll 30 patients onto the trial, with goal of at least 24 evaluable patients accrued.

In the run-in phase, a total of 6 evaluable patients will be accrued to receive Flutamide administration. We will use a Bayesian monitoring rule to determine if the study is feasible. Specifically, we would consider it is “infeasible” if the probability of not observing greater than or equal to 5% of prostate cancer cells having gammaH2AX foci is more than 50%. Based on the Bayesian monitoring rule in Section 6.3, if there is less than or equal to 1 out of 6 cases with detectable DNA double strand breaks (i.e., greater than or equal to 5% of prostate cancer cells having gammaH2AX foci on patient level), the study will be considered as infeasible and will not proceed into the randomization part.

If the study proceeds into the randomization part, a total of 18 evaluable patients will be randomized in a 2:1 ratio to either receive Flutamide (12 patients) or not (6 patients). A total of 18 patients treated with Flutamide (6 from run-in and 12 from randomization) will produce a two-sided 90% confidence interval with a width ranging from 0.35 to 0.42 (if the true proportion of prostate cancer cells having gammaH2AX foci is 30%-80%). A total of 6 patients in control will produce a two-sided 90% confidence interval with a width approximately less than 0.5 (if the true proportion of prostate cancer cells having gammaH2AX foci is less than 10%).

All eligible patients will be offered enrollment on the study, and we estimate a 20% dropout and nonevaluable rate. Patients who drop out prior to the biopsy/brachytherapy procedure will be replaced; patients who drop out after biopsy/brachytherapy will not be replaced. In order to ensure at least 24 evaluable patients are available, we plan to enroll ~30 patients onto this trial. Given the minimal addition to standard therapy and effort requirement from patient, we expect to accrue at least 2-3 patients/month, and the full accrual will be completed in 2 years.

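### Six single-arm run-in biopsies are pooled into the flutamide estimate without a masked common reading or a randomised-only comparison, leaving the contrast with placebo open to reader and staining-run differences

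*Combined protocol and SAP*

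**What the plan says.** Section 4.0 sets up the first phase: "The initial phase is a 6-patient single-arm run-in phase to test feasibility and rule out futility of the intervention". Treatment in that phase is fixed by design: "All patients within the run-in phase will receive 250mg Flutamide prior to brachytherapy and prostatic biopsy". The result decides whether the second phase opens: "If futility is ruled out (>1 patients with DSBs on biopsy), then accrual will continue in the randomized, double-blind phase". Sections 6.2 and 6.3 repeat the gate, stopping at one or fewer of six.

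For the second phase, Section 6.2 says that "a total of 18 evaluable patients will be randomized in a 2:1 ratio to either receive Flutamide (12 patients) or not (6 patients"). It then pools across phases: "A total of 18 patients treated with Flutamide (6 from run-in and 12 from randomization) will produce a two-sided 90% confidence interval", with a stated width of 0.35 to 0.42. Section 6.3 also counts the six run-in patients in its continuous stopping rule for 18 flutamide patients.

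The primary objective in Section 2.0 is comparative, flutamide against placebo. The reading is the share of cancer cells with gammaH2AX foci, cut at 5% per patient (Sections 6.1 to 6.3).

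On the laboratory side, Section 5.3 says "Analyses for DSBs will be performed using assays for TUNEL, 53bp1, and gamma h2ax", and it covers paraffin embedding, freezing of about one third of the tissue, and archiving. It does not mention coded slides, reader masking, staining batches or a joint re-read.

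**The concern.** The flutamide group draws on two phases and the placebo group on one, so phase is partly confounded with arm. The phases differ in two ways that can affect a scored tissue reading. In the run-in there is only one treatment, so anyone who knows a slide is from the run-in knows the drug was given. The run-in slides must also be read earlier than any placebo slide, which makes a different staining run or a drift in scoring practice possible.

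Any such difference enters the flutamide side of the primary contrast and not the placebo side. Section 6.2 says the pilot will be used to design a larger study, so an error in the contrast would carry forward.

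**Working it through.** **Inputs.** Run-in: 6 patients, all on flutamide (4.0). Randomised: 12 flutamide, 6 placebo (6.2). Pooled flutamide: 6 + 12 = 18 (6.2). Interval: two-sided 90% (6.2). Patient-level cut: 5% of cells (6.1 to 6.3). The documents give no figure for a reading or batch shift.

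**1. Reproduce the stated precision.** Use the exact (Clopper-Pearson) 90% interval at x = n·p:
- lower limit = Beta quantile at 0.05 with parameters (x, n − x + 1)
- upper limit = Beta quantile at 0.95 with parameters (x + 1, n − x)

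| True proportion | Width, n = 18 | Width, n = 12 |
|---|---|---|
| 30% | 0.389 | 0.476 |
| 50% | 0.418 | 0.509 |
| 80% | 0.348 | 0.429 |

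With n = 18 the range is 0.35 to 0.42, the plan's own figure. The normal-approximation interval gives 0.31 to 0.39 and does not match. For six controls, the expected exact width is 0.444 at 5% and 0.488 at 10%, in line with the plan's figure of roughly under 0.5. With the 12 randomised flutamide patients alone the range would be 0.43 to 0.51, so the stated precision depends on pooling the run-in.

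**2. Share of readings exposed.** Flutamide: 6/18 = 33%. Placebo: 0/6 = 0%.

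**3. What a run-in-only difference would do.** Two scales matter, because Section 6.2 names a share of cells while its widths reproduce as a binomial interval on patients.
- *Mean share of positive cells.* A shift of d points confined to the run-in moves the pooled flutamide mean by d × 6/18 = d/3. Assumed values of d = 10, 20 and 30 points give 3.3, 6.7 and 10 points. Placebo moves by 0.
- *Patients at or above 5%.* The d/3 formula does not apply here. Only patients near the cut can change class, and each run-in patient reclassified moves the pooled proportion by 1/18 = 5.6 points; two move it by 2/18 = 11.1 points.

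On either scale the 12 versus 6 comparison moves by 0.

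**4. Precision of the contrast.** Assume 50% on flutamide and 10% on placebo, with a normal-approximation 90% interval of width 2 × 1.645 × √(p₁q₁/n₁ + p₂q₂/n₂):
- 18 versus 6: 3.29 × √(0.25/18 + 0.09/6) = 0.56
- 12 versus 6: 3.29 × √(0.25/12 + 0.09/6) = 0.62

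In this example, dropping the run-in from the contrast costs little, because the six placebo patients contribute much of the variance.

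**5. The gate.** One or fewer of 6 with breaks stops the study; 2 of 6 continues. A 2 of 6 result means 4 without detectable breaks. Table 6.3.1 calls for suspension at 5 of 7, so one further flutamide patient without detectable breaks would trigger it.

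**The case against.** The strongest reply is that the documents are silent on reader masking, and silence is not evidence of unmasked reading. A reader might infer that everyone scoring the run-in knew the treatment and that the pooled result is therefore biased upward. Section 5.3 does not say who reads the slides or what they know, so that inference is not supported. What stands is that no provision prevents such knowledge.

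A reader might also infer a clean contrast between unmasked run-in readings and blinded randomised ones. Section 4.0 calls the second phase double-blind without saying whether this covers slide readers. The Section 6.3 rule also requires someone to link results to flutamide patients as they accrue. The same rule implies that randomised slides are read over time, so early versus late may be only one of several run differences.

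A third tempting inference is that misreading would push a futile study through the gate. That would need borderline patients misread in one direction, and the continuous rule limits the harm, as step 5 shows.

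Finally, this is a pilot justified by interval width, with no powered between-arm test, and the pooling is openly declared. That lowers the weight of the point. It does not remove it, because the primary objective is still a comparison with placebo and neither a common reading nor a randomised-only analysis is planned.

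**Conclusion.** The point holds as an open route to bias, not as demonstrated bias. The structure follows from the text: single-arm run-in biopsies are scored first and then pooled, with placebo patients only in the later phase. One third of the flutamide readings and none of the placebo readings are exposed. The effect on the contrast is d/3 on the mean-cell-share scale, or 1/18 per reclassified patient on the 5% scale. The value of d, its sign and the number of borderline patients are assumptions, since the documents give none of them.

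The plan should address this, since it affects the primary contrast and is cheap to close. It does not invalidate the pilot or its stated 18-patient precision.

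**What to change.** 1. **Sections 5.3 and 6.1.** State that, for the final estimates, the gammaH2AX slides of all evaluable patients from both phases are coded, put in random order and re-read once by the same laboratory, masked to arm and phase. Restain in a common batch only where enough paraffin tissue remains. Readings made during accrual continue to serve the run-in gate and the Table 6.3.1 rule.
2. **Section 6.2.** Report the randomised-only comparison, 12 flutamide versus 6 placebo, beside the pooled 18-patient estimate.

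The two parts complement each other. The re-read addresses reader knowledge and scoring drift in both phases, but without restaining it leaves staining-run differences in place. The randomised-only comparison takes the run-in out of the contrast and uses no tissue.

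**Cost.** Slide coding and one further read, with no new reader, biopsy or patient. Restaining would use tissue from more than the six run-in blocks, because randomised flutamide samples will already have been stained for monitoring. Tissue is limited: about one third is frozen and three assays are planned. The 18-patient width is unchanged by a re-read. The randomised-only flutamide estimate has a 90% width of about 0.43 to 0.51 against 0.35 to 0.42 pooled.
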